### **Treatment-emergent Laboratory Abnormality**

A treatment-emergent laboratory abnormality is defined as value outside the normal range which occurs on or after the start of IMP and up to the follow-up contact following discontinuation of IMP of a given analysis period.

In Part A, treatment-emergent laboratory abnormalities will be attributed to a period based on the start date. A laboratory abnormality occurring on or after the initiation of IMP in Period 1 and before dosing with IMP for Period 2, or through the follow-up contact if subject discontinues prior to Period 2, is considered a Period 1 laboratory abnormality. For Cohort 1 and 2, a laboratory abnormality occurring on or after the initiation of IMP in Period 2 and before dosing with IMP for Period 3, or through the follow-up contact if subject discontinues prior to Period 3, is considered a Period 2 laboratory abnormality. A laboratory abnormality occurring on or after the initiation of IMP in Period 3 and before dosing with IMP for Period 4, or through the follow-up contact if subject discontinues prior to Period 4, is considered a Period 3 laboratory abnormality. A laboratory abnormality occurring after dosing for Period 4 through the follow-up contact is considered a Period 4 treatment-emergent laboratory abnormality.

### **Treatment-emergent Laboratory Toxicity**

A treatment-emergent laboratory toxicity is defined as an increase of at least one toxicity grade from the baseline assessment at any post baseline visit. The post baseline visit must occur after the administration of IMP and through the follow-up contact. For defining treatment-emergent laboratory events, it is assumed that a laboratory assessment obtained on Day 1 with missing collection times occurred prior to the initiation of IMP unless a protocol deviation is identified. If the relevant baseline assessments are missing, then any graded toxicity (ie, at least Grade 1) is considered treatment-emergent.

For Part A, treatment-emergent laboratory toxicities will be attributed to a period based on the start date. A laboratory toxicity occurring on or after the initiation of IMP in Period 1 and before dosing with IMP for Period 2, or through the follow-up contact if subject discontinues prior to Period 2, is considered a Period 1 treatment-emergent toxicity. For Cohort 1 and 2, a laboratory toxicity occurring after dosing for Period 2 and before dosing with IMP for Period 3, or through the follow-up contact if subject discontinues prior to Period 3, is considered a Period 2 treatment-emergent toxicity. A laboratory toxicity occurring on or after the initiation of IMP in Period 3 and before dosing with IMP for Period 4, or through the follow-up contact if subject discontinues prior to Period 4, is considered a Period 3 laboratory toxicity. A laboratory toxicity occurring after dosing for Period 4 through the follow-up contact post Period 4 is considered a Period 4 treatment-emergent toxicity.

### **Columbia-Suicide Severity Rating Scale (C-SSRS)**

The C-SSRS is comprised of 10 categories with binary responses. Details of the assessments and definitions are provided in [Appendix 9.2](#).

## Overdose

An overdose is defined as a known deliberate or accidental administration of investigational drug, to or by a trial participant, at a dose above that which is assigned to that individual participant according to the protocol.

## Concomitant Medications

Concomitant medications are those medications taken on or after the initiation of IMP. These medications include those medications started before the initiation of IMP and continuing post Day 1. Concomitant medications will be classified by treatment. Medications taken during a washout period will be applied to the treatment received immediately prior. Medications taken across multiple treatments will be assigned to those treatments. These medications will be recorded in the Concomitant Medications page of the eCRF.

## Prior Medications

Prior medications are those medications taken prior, and ended prior, to the first initiation of IMP. Medications and therapies are to be recorded in the eCRF if taken by the subject at any time 30 days prior to signing of informed consent.

### **Orthostatic Vital Sign Change**

Orthostatic change for blood pressure and heart rate is calculated as the difference in the standing value from the supine value (ie, supine value – standing value) both collected at the same visit, date, and timepoint.

The image consists of several large, solid black rectangular blocks of varying sizes. These blocks are arranged in a way that suggests a layered or overlapping effect. The most prominent block is a large rectangle at the top, with a smaller one nested within its lower right corner. Below these, there is a large horizontal rectangle in the center, flanked by two smaller vertical rectangles on the left. In the bottom right corner, there is a small, isolated white shape that resembles a stylized 'T' or a cross. The overall composition is abstract and minimalist, using only black and white colors and geometric shapes.

[REDACTED]

[REDACTED]

[REDACTED]

[REDACTED]

[REDACTED]

### **Loss to Follow-Up**

A participant will be considered lost to follow-up if he/she repeatedly fails to return for scheduled visits and is unable to be contacted by the trial site personnel.

### **Study Withdrawal**

A participant is considered to have withdrawn from the study if they withdraw their consent from further participation in the trial at any time. The investigator can also discontinue a subject's participation in the trial at any time if medically necessary. If a subject is determined to be lost to follow-up, he/she will be considered to have withdrawn from the trial. Participants cannot withdraw consent for use of data already collected as part of the trial, but only for future participation.

### **Completed Subject**

A participant is considered to have completed the trial if he/she has completed all periods of the trial including the last in-clinic visit (Day 3 in Period 4 [Part A] or Day 17 [Part B]), as shown in the Schedule of Assessments ([Appendix 9.1](#)).

### **End of Trial**

The end of the trial is defined as the date of the last visit (including phone contact) of the last participant in the trial.

### **End of Period**

For purposes of analysis of data within each study period, the End of Period value will be defined as the last valid evaluation done before the IMP administration for the next period. For the last period in the study, there will be no end of period value. For [REDACTED], ECG, Lab, and Vital tables, End of Period values will not be presented.

## **4.2. Visit Windows**

### **4.2.1. Method of Aligning Measurements to Treatment for Part A (SAD)**

Given the crossover nature of Part A, measurements will be assigned to treatment based on treatment received at each analysis period. The start of a given analysis period will be defined as the time in which a subject takes the first dose of IMP for that analysis period. The end of the

analysis period will be the last measurement taken prior to the start of the next analysis period or the end of the study.

Measurements taken on or after the initiation of IMP in Period 1, and before dosing with IMP for Period 2, or through the end of the study if Period 2 dosing is not initiated, are considered Period 1 measurements, and will be assigned to the treatment randomized or received in Period 1, as appropriate. Measurements taken on or after the initiation of IMP in Period 2, and before dosing with IMP for Period 3, or through the end of the study if Period 3 dosing is not initiated, are considered Period 2 measurements, and will be assigned to the treatment randomized or received in Period 2, as appropriate. Measurements taken on or after the initiation of IMP in Period 3, and before dosing with IMP for Period 4, or through the end of the study if Period 4 dosing is not initiated, are considered Period 3 measurements, and will be assigned to the treatment randomized or received in Period 3, as appropriate. A measurement taken after initiation of dosing for Period 4 is considered a Period 4 event and is assigned to the treatment randomized or received in Period 4, as appropriate.

The 12-lead ECG and vital sign measurements performed pre-dose on Day 1 of each period will serve as the period-specific baseline. For safety laboratory tests, C-SSRS, and vital sign measurements (standing heart rate and blood pressure) not performed pre-dose on Day 1, the assessment performed on the check-in day (Day -1) for each period serves as the baseline value for that period. For [REDACTED] the Predose value for a specific period will serve as the Period Baseline. [REDACTED]

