4.1.4. Definition of Completed Participant

A participant is considered to have completed the trial if he/she has completed all periods of the trial including the last in-clinic visit (Day 3 in Period 4 [Part A, Cohorts 1 and 2], Day 3 in Period 2 [Part A, Cohort 3]), or Day 17 [Part B]), as shown in the Schedule of Assessments in Section 1.3.

A participant who completed all procedures except the follow-up contact would therefore not be considered an early termination participant.

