## 5. STATISTICAL ANALYSIS METHODS

### 5.1. General Considerations

Descriptive statistical methods will be used to summarize the data from this study. No formal hypothesis testing is planned for this trial. Unless stated otherwise, the term “descriptive statistics” refers to number of subjects (N), number of observations (n), mean, median, standard deviation (SD), Q1, Q3, minimum, and maximum for continuous data and frequencies and percentages for categorical data. Figure presentations will include appropriate variability indicator such as SD or standard error (SE).

All data collected during the study will be included in data listings. Unless otherwise noted, the data presentations will be sorted first by trial part (A or B), cohort, and subject number. Unless otherwise noted, summary tables will be separated into Part A Cohorts 1 and 2, Part A Food Effects, and Part B.

In Part A, the term “treatment sequence” refers to the sequence of treatment for each individual. “Treatment group” refers to treatment with CVL-354, at different doses, or placebo. Since Part A is a crossover study, subjects will appear in multiple groups. For Part A Cohorts 1 and 2, “Treatment period” refers to Periods 1 through 4 described in [Figure 1](#). For Part A Food Effects, “Treatment period” refers to Period 1 and 2 described in [Figure 2](#).

In Part B, “treatment group” refers to treatment with CVL-354, at different doses, or placebo QD or BID. Doses will be determined based on data from Part A.

For summary presentations, placebo subjects will be combined across cohorts within a given Part.

The statistical analyses will be conducted with the SAS® software package Version 9.4 or higher.

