## 5.6. Subject Disposition, Demographic and Baseline Characteristics

Subject disposition will be presented for all screened subjects. The number of subjects who were screened, met all eligibility criteria, as well as the number of subjects included in different Analysis sets will be presented. Screen failures and reason for failure will be presented. The number of subjects who completed the study and discontinued from the study will be provided, as well as reason for discontinuation. Additionally, the number of days on study will be summarized. Data will be presented by cohort for Part A Cohorts 1 and 2, sequence for Part A Food Effects, and treatment group for Part B. For Part A Cohorts 1 and 2, a separate presentation by sequence will be provided.

Demographic data and baseline characteristics including age, sex, childbearing potential, ethnicity, height, weight, body mass index (BMI) will be summarized using descriptive statistics with respect to randomized population. Data will be presented by cohort for Part A Cohorts 1 and 2, sequence for Part A Food Effects, and treatment group for Part B. For Part A Cohorts 1 and 2, a separate presentation by dose will be provided.

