- k A one-time baseline report of continuous ECG telemetry will be recorded for each participant by the site for a minimum of 12 hours starting on Day -1 prior to first dose. This baseline report will also be required for replacement participants.
- l Continuous ECG will be recorded for a minimum of 26 hours, starting at least 2 hours predose and continuing until 24 hours postdose. Electrocardiograms will be extracted from the continuous recording by a central ECG service from the following time points: -45, -30, and -15 minutes predose, and 0.5, 1, 2, 3, 4, 8, 12, and 24 hours postdose. Participants should be resting quietly in a supine position for at least 10 minutes before and 5 minutes after each extraction time point.
- m Triplicate ECGs will be obtained to confirm eligibility at Screening. Single ECGs will be obtained at all other time points.
- n Blood pressure and heart rate measurements will be obtained from participants in a supine position after at least 3 minutes of rest.
- o Orthostatic blood pressure and heart rate measurements will be obtained from participants in the standing position.
- p The "Baseline/Screening" C-SSRS form will be completed for all participants at Screening to determine eligibility. The "Since Last Visit" C-SSRS form will be completed at Check-in for each period to ensure that the participant continues to qualify for the trial and will also be completed at Check-out (or ET).
- q Concomitant medications should be recorded from Screening through the participant's last visit/contact.
- r Adverse events (serious and nonserious) will be recorded from first dose of IMP through the participant's last visit/contact. This also applies to replacement participants.
- s Additional urine drug screening can be conducted at any time during the trial at the discretion of the investigator.
- t A confirmatory FSH is required for all post-menopausal women.
- u Predose PK samples (1 sample and 1 backup sample) will be obtained within 15 minutes prior to dosing.
- v Future biospecimen research sample is optional and is only to be collected if signed consent is obtained from the participant. Sample can be collected at any time prior to initiation of first dose.

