a Contact with participant via phone call, internet/web, or other acceptable means of communication to check on their status 14±3 days after their final dose of IMP in the trial.

b Participants must have COVID-19 testing done with a negative test result within a maximum of 5 days prior to, but as close as possible to, admission to the clinic. COVID-19 testing may be performed after admission per the investigator's discretion.

c The treatment phase will comprise 2 periods with a 2-day washout between Periods 1 and 2. Participants will be discharged from the clinic on Period 2 Day 3 (Check-out).

d Predose assessments to be completed within 60 minutes of dosing unless otherwise noted.

e Medical occurrences that begin before the start of IMP dosing but after obtaining informed consent will be recorded as medical and/or psychiatric history.

f An alcohol test (breathalyzer or blood/urine) is required at Screening and at Check-in. The alcohol test may be conducted at any time during the trial at the discretion of the investigator.

g Period 1 only.

h Full physical and neurological examinations should be completed at Screening and Check-out (or ET). A limited examination (cardiovascular, pulmonary, and gastrointestinal) should be completed at Check-in. Symptom driven physical and/or neurological examinations may be done at any time point during the trial at the investigator's discretion.

i Triplicate ECGs will be obtained to confirm eligibility at Screening. Single ECGs will be obtained at all other time points.

j Blood pressure and heart rate measurements will be obtained from participants in a supine position after at least 3 minutes of rest.

k Orthostatic blood pressure and heart rate measurements will be obtained from participants in the standing position.

l The "Baseline/Screening" C-SSRS form will be completed for all participants at Screening to determine eligibility. The "Since Last Visit" C-SSRS form will be completed at Check-in to ensure that the participant continues to qualify for the trial and will also be completed at Check-out (or ET).

m Concomitant medications should be recorded from Screening through the participant's last visit/contact.

n Adverse events (serious and nonserious) will be recorded from first dose of IMP through the participant's last visit/contact.

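### Two SAP rules for Part A were not adapted to the two-period food-effect cohort: the completer definition names Period 4, and the Period 2 baseline for standing vital signs and laboratory tests falls back on Period 1 postdose values

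*SAP*

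**What the plan says.** **Completion.** SAP Completed Subject requires all periods including the "last in-clinic visit (Day 3 in Period 4 [Part A] or Day 17 [Part B]), as shown in the Schedule of Assessments". It makes no exception for Cohort 3. Protocol 4.1.4 does, and gives "Day 3 in Period 2 [Part A, Cohort 3" as that cohort's endpoint. Elsewhere the SAP knows that Cohort 3 is different: for Food Effects, SAP 5.1 says that treatment period "refers to Period 1 and 2 described in" Figure 2, and SAP Table 5 footnote c states "Participants will be discharged from the clinic on Period 2 Day 3 (Check-out". The definition is used, because SAP 5.6 says "The number of subjects who completed the study and discontinued from the study will be provided", by sequence for Food Effects.

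**Baseline.** SAP 4.2.1 takes the period baseline of ECG and vital signs from the Day 1 predose measurement. For assessments without one (safety laboratory tests, C-SSRS, standing heart rate and blood pressure), "the assessment performed on the check-in day (Day -1) for each period serves as the baseline value for that period". The general definition, Period Baseline Value (Part A), takes the last valid evaluation before dosing in each period and is not limited to any cohort.

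**Check-ins.** The C-SSRS footnotes show the difference between the schedules. For Cohorts 1 and 2 (SAP Table 4), the "C-SSRS form will be completed at Check-in for each period to ensure that the participant continues to qualify for the trial". For Cohort 3 (SAP Table 5), the "C-SSRS form will be completed at Check-in to ensure that the participant continues to qualify for the trial", with no mention of each period. SAP 1.1.2 keeps Cohort 3 participants in the clinic from Check-in through both periods.

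**The concern.** The SAP states that it is based on Protocol Version 3.0, yet its completer definition does not carry that version's Cohort 3 endpoint. The rule as written contradicts the protocol for one of the three Part A cohorts.

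For the baseline, the specific rule points to a Period 2 check-in that is not on the Cohort 3 schedule. What is left is the general rule, and it leads to values taken after the first active dose. All Cohort 3 participants receive 50 mg in both periods and there is no placebo, so change from baseline is a main safety reference within this cohort. If the Period 2 baseline is itself an on-drug value at the same postdose hour, an effect present in both periods can disappear from the Period 2 change.

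**Working it through.** **1. Calendar.** Inputs: 3 days per period and a 2-day washout (SAP 1.1.2); Check-out on Day 8 (Protocol Figure 2); follow-up on Day 20 (Protocol Table 2).
- Period 2 dose: 3 + 2 + 1 = Day 6.
- Period 2 Day 3: 6 + 2 = Day 8, which reproduces the stated Check-out.
- Follow-up: 6 + 14 = Day 20, which reproduces the stated contact day.
- A Period 2 Day -1 would be Day 5. That is a washout day with nothing scheduled.

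**2. Completers.** Cohort 3 ends at Period 2 Day 3. Read literally, the SAP rule gives 0 of about 8 completers; the protocol rule allows up to 8 of 8. Part A has 8 + 8 + 8 = 24 participants, so the rule does not fit about one third of them.

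**3. Is there a Period 2 source under SAP 4.2.1?** In SAP Table 5 the only Day -1 column stands under Screening, outside the block headed Periods 1 and 2. The predose column has ECG, supine vital signs, respiratory rate and temperature. It has no laboratory tests and no standing vital signs. So the named source does not exist for Period 2.

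**4. What does the general rule give?** One could read it as requiring the evaluation itself to fall inside the period. But SAP 4.1.2.2 and 4.2.1 start each period at dosing, so on that reading no predose value could be a baseline in any cohort. The End of Period definition uses parallel wording and plainly means the last value before the next dose. Read that way, with 5 x 24 = 120 h between the doses on Day 1 and Day 6:

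| Assessment | Last scheduled value before the Period 2 dose | Interval to that dose |
|---|---|---|
| Standing heart rate and blood pressure | Period 1, 2 h postdose | 120 - 2 = 118 h |
| Safety laboratory tests | Period 1, 48 h postdose | 120 - 48 = 72 h |
| ECG, supine vital signs | Period 2 predose | not affected |

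**5. What that does to the 2 h change.** As an illustration only, let *m* be the undosed standing value and let the dose shift it by *d* at 2 h in both periods, fed or fasted, with no carryover.
- Period 1 change: (*m* + *d*) - *m* = *d*.
- Period 2 change: (*m* + *d*) - (*m* + *d*) = 0.
- With 4 participants per sequence (Protocol Figure 2) and the two periods pooled within each food condition, the mean change is (4*d* + 4 x 0)/8 = *d*/2.
- With the Day -1 value as baseline in both periods, it is *d*.

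Orthostatic change (supine minus standing) behaves in the same way. The documents give no *d*, so the effect on the actual tables cannot be computed.

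**6. Which outputs use these baselines?** SAP 5.9.5 tabulates change from period baseline for vital signs, including orthostatic change. SAP 5.9.4 uses period baseline for laboratory shifts. Its by-day laboratory summaries and multiples of the upper limit of normal need no baseline value.

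**7. Age of the Day -1 value.** Day -1 to Day 1 is 1 day and Day 1 to Day 6 is 5 days, so it is about 6 days old at the Period 2 dose.

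**The case against.** **Completion is only a wording slip.** The definition points to the Schedule of Assessments, which ends Cohort 3 at Period 2 Day 3, and Days on Study takes the completion date from the End of Study eCRF page. This stands as far as it goes. A reader might infer that the disposition table will show no Cohort 3 completers; the documents do not support that, because the intent can be recovered. The stated rule still contradicts the protocol.

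**A baseline rule does exist.** A reader might infer that Period 2 has no stated baseline at all. That goes too far: the general Part A rule is stated, and its sensible reading gives a computable value. The problem is which value it gives.

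**C-SSRS.** SAP 4.2.1 names C-SSRS beside the other two assessments, so a reader might infer that its results are affected too. No named output is. SAP 5.9.7 summarises maximum results without subtracting a baseline, and the emergence categories have their own baseline in SAP Appendix 9.2. Footnote l of Table 5 may also mean that the last C-SSRS before Period 2 is the Day -1 one.

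**Laboratory toxicity.** The SAP counts any graded toxicity as treatment-emergent if the baseline is missing. This covers graded tests if the Period 2 baseline is treated as missing, and it makes the laboratory part secondary.

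**Redaction and heading.** The SAP 4.2.1 paragraph ends in blacked-out text, and the section heading says (SAD). The gap may be filled there, or the section may not be meant for Cohort 3, although SAP 5.9 sends all of Part A to it for treatment assignment. If Cohort 3 is excluded, the general rule is again what remains. This limits confidence.

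**Period baselines always follow an earlier dose.** That is true in Cohorts 1 and 2 as well. There, however, the check-in value is taken shortly before the next dose, with at least 5 days between doses. In Cohort 3 the standing value dates from 2 h after the previous dose.

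**Conclusion.** The point holds and is minor.

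- **Completer definition:** wrong as written for about 8 of about 24 Part A participants and in conflict with Protocol 4.1.4. This is certain from the text.
- **Period 2 baseline:** moderate confidence, because it rests on the visible text and on the reading of the general rule in step 4. The main effect is on the Period 2 standing and orthostatic change at 2 h for about 8 participants. The secondary effect is on their Period 2 laboratory shifts.

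Everything affected is descriptive. The PK food-effect model, treatment-emergent adverse events, ECG and supine vital signs do not depend on these rules.

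**What to change.** 1. **SAP Completed Subject:** adopt the Protocol 4.1.4 wording, with separate endpoints for Part A Cohorts 1 and 2 (Period 4 Day 3), Part A Cohort 3 (Period 2 Day 3) and Part B (Day 17).
2. **SAP 4.1.2.4 and 4.2.1:** state that for Cohort 3 the single Day -1 Check-in value is the baseline for both periods for standing heart rate and blood pressure (including orthostatic change) and for safety laboratory shifts. Supine values are also taken at that Check-in, so an orthostatic baseline can be formed.
3. **Table footnote:** this baseline is about 6 days old at the Period 2 dose, and a Period 1 change that persists also counts in Period 2.

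SAP 4.1.2.2 also describes four treatments for all of Part A and can be corrected at the same time.

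The cost is SAP wording and one footnote, with no new assessments. There are two drawbacks. A persistent Period 1 change would also be counted under the other food condition. Cohort 3 tables would also mix baseline types, since ECG and supine vital signs keep their period-specific predose baselines.
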